## 2.6 Sample Size Consideration

In a recent antiviral drug trial to treat adults hospitalized with severe COVID-19 published in the New England Journal of Medicine (NEJM) on March 18, 2020^32, the results showed that a mortality rate of 17%, hospital stay rate of 50%, and ECMO or mechanical intubation rate of 11% among the patients managed with BSC after two-week follow-up. In the current study, we propose a composite endpoint of mortality, ongoing need for hospitalization, and ECMO or mechanical intubation at 15 days after randomization. We are expecting to reduce the composite endpoint rate to 35% after the degarelix treatment plus BSC from 60% for patients treated placebo plus BSC.

The sample size estimation and power analysis shown in Table 2 are based on the hypothesis testing of the primary endpoint, which is the composite endpoint of mortality, hospital stay rate, and ECMO or mechanical intubation at 15 days after

randomization (Day 15). According to the composite endpoint outlined in the previous section, we assume that an effect size for the primary endpoint of 42% can be anticipated in the degarelix group. The other assumptions include a three-month accrual time and one-month follow-up time, and 2:1 sample allocation of degarelix: placebo treatment group. The sample size for the study is estimated based on a superiority trial design. To have 90% power of detecting the expected 42% reduction using a two-sided two proportion test with a significance level of 0.05 in the degarelix compared to the placebo group will require 186 evaluable patients total (i.e. 124 evaluable patients in the degarelix group and 62 evaluable patients in the placebo group). Based on an assumed 5% attrition rate, 198 patients will be required (i.e. 132 in the degarelix group and 66 in the placebo group) to achieve actual statistical significance at alpha level of 0.05 and power of 90% (Appendix 5.5).

## 3.0 STATISTICAL METHODS

### 3.1 Statistical Handling Policy

#### 3.1.1 Missing Data and Imputations

Every effort will be made to minimize the occurrence of missing data, particularly for the primary and the secondary endpoints. In the event of a potential drop out, every effort will be made to capture missed data from the patient record and VA databases. For patients who drop out during the study the missing values for the primary endpoint analysis will be considered as failures. However multiple imputation (MI) method may be used for certain secondary endpoint analyses. Multiple imputations will be performed using SAS PROC MI under missing at random assumption. If the assumption does not hold, then imputations will be performed. Sensitivity analysis will be performed to compare the results from the various imputation scenarios.

#### 3.1.2 Analysis Conventions

This section details general policies to be used for the statistical analyses. Departures from these general policies may be given in the specific detailed sections of this statistical analysis plan. When this situation occurs, the rules set forth in the

specific section take precedence over the general policies. The following policies will be applied to all data presentations and analyses.

- All statistical tests will use a significance level of  $\alpha = 0.05$ . Two-tailed tests will be performed for all analyses that use statistical testing.
- All p-values will be rounded to 3 decimal places. All p-values that round to 0.000 will be presented as ' $<0.001$ ' and p-values that round to 1.000 will be presented as ' $>0.999$ '. Any p-value  $\leq \alpha$  will be considered statistically significant.
- Summary statistics will consist of the number and percentage of responses in each category for discrete variables, and the mean, median, standard deviation (SD), minimum, and maximum for continuous variables.
- All mean and median values will be formatted to one more decimal place than the measured value. Standard deviation values will be formatted to two more decimal places than the measured value.
- All percentages will be rounded to one decimal place. The number and percentage of responses will be presented in the form XX (XX.X), where the percentage is in the parentheses. The decimal of the percentage may be dropped due to space constraints when creating a table.
- All listings will be sorted for presentation in order of treatment group, site number, participant number, and date of procedure or event.
- All analysis and summary tables will have the population sample size for each treatment group in the column heading.
- Calculating change from baseline to a visit will be done as follows: change = visit –baseline.
- Baseline is defined as the last data point before the first treatment is administered. If baseline data are not available, screening data will be used.
- Version 9.4 of SAS® or higher will be the statistical software package used to produce all summaries, listings, statistical analyses, and graphs.
- Updated version of MedDRA will be used for adverse event and pre-treatment coding.

- The current version of the World Health Organization (WHO) drug dictionary will be used for the coding of medications.

### 3.2 Participant Disposition

Participant disposition will be summarized for the ITT population.

- The number and percentage of participants who completed or discontinued prematurely from the study by treatment group will be tabulated and tested using Pearson  $\chi^2$  test (Table 3.2.1). The number and percentage of participants who completed or discontinued prematurely in each treatment group will also be displayed graphically (Figure 3.2.1).
- The number and percentage of participants who discontinued for each reason will be presented by treatment group (Table 3.2.2).
- A listing of participants that discontinued prematurely from the study will be presented. The listing will include information about treatment, study center, participant number, age, race, number of days, and reason for discontinuation (Table 3.2.3).
- The number and percentage of participants who completed or discontinued prematurely from the study by study center will be tabulated and tested using Pearson  $\chi^2$  test (Table 3.2.4). The number and percentage of participants who completed or discontinued prematurely in each treatment group will also be displayed graphically (Figure 3.2.1).

### 3.4 Study Protocol Adherence

Study treatments and adherence will be summarized by treatment group and overall for the ITT population. The number and percentages of participants will be presented for each treatment group and overall (Table 3.4.1). The number and percentage of non-adherence participants will be summarized by the treatment groups and tested using Pearson  $\chi^2$  test. The following information will be presented for each treatment group and overall for adherence:

- Summary of protocol non-adherence (Table 3.4.2)
- Summary statistics (number of participants, mean, median, SD, minimum, and maximum) for study adherence (Table 3.4.3)

### 3.5 Participant Demographics and Characteristics

The patient demographics and pre-treatment baseline characteristics and medical history will be summarized for each treatment group and overall for the ITT population. For continuous variables, the sample size, mean, median, SD, minimum, and maximum value will be calculated and tested either by Student t or Wilcoxon test depending on data distributions using SAS PROC TTEST and SAS PROC NPAR1WAY, respectively. For categorical variables, the number and percentage of patients by the treatment group will be tabulated and tested based on Pearson  $\chi^2$  test using SAS PROC FREQ.

#### 3.5.1 Demographics

The summary of demographics at baseline will include age, race, gender, ethnicity, marital status, military history, location of military service, branch of service, and pre-admission residence (Tables 3.5.1).

### **3.5.2 Baseline Characteristics**

Baseline comparability among the treatment groups will be evaluated by providing a summary of baseline test results (D-dimer, IL-6, LDH, ferritin, total WBC, absolute neutrophil count (ANC), absolute lymphocyte count (ALC), hemoglobin, hematocrit, platelet counts, and testosterone) and baseline medical status (fever, oxygen needs, and days symptoms started prior to hospitalization) (Tables 3.5.2).

### **3.5.3 Medical History**

The number and percentage of participants reporting a medical history will be summarized by the following medical conditions: COPD, hypertension, cardiovascular disease, asthma, diabetes, use of angiotensin converting enzyme inhibitors within last 30 days prior to hospitalization, and use of supplemental oxygen prior to hospitalization (Tables 3.5.3).

## **3.6 Concomitant Medications**

Summaries for prior and concomitant medications will be done for the ITT population. Concomitant medications will be reported at screening, day 8,15,22, and 30. Each summary below will be done for each treatment group and for all participants:

- Prior medications – medications taken prior to the study drug administration
- Concomitant medications –medications taken on or after the study drug administration

All medications recorded on the CRF will be coded to the therapeutic drug classes and generic drug names using the World Health Organization (WHO) drug classifications. The current version of the WHO drug dictionary will be used for the coding of medications.

The number and percentage of participants who take medications that are coded to each generic drug name and therapeutic drug class will be tabulated by the treatment group and tested based on Pearson  $\chi^2$  test using SAS PROC FREQ (Tables 3.6.1-2). If there are significant differences between the two treatment groups for certain study related drugs, these concomitant medication use will be adjusted for the endpoint efficacy analyses when it is necessary.

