### 3.7 Efficacy Analyses

The primary analysis of the study will be performed on the primary endpoint on the ITT population. The secondary analyses will be performed on the ITT population and available data. Both the primary and secondary endpoints analyses will be performed for the hypothesis testing. While the exploratory endpoints will be analyzed to generate new hypothesis unless otherwise specified. Potential difficulties of convergence of model fit, which arise in efficacy analyses that include covariates, will be handled using the method described in section 3.7.1. The analysis plan is summarized in the Appendix 5.6.

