#### 3.7.1. Primary Endpoint Analysis

The primary study endpoint will be the composite outcome of mortality, ongoing need for hospitalization, and ECMO or mechanical intubation at 15 days after randomization. This outcome will be compared according to assigned treatment groups, using Pearson  $\chi^2$  test. The test for differences between the treatment groups in the primary outcome will be conducted at an overall  $\alpha$ -level of 0.05 (i.e.  $\alpha = 0.006$  for mid-term interim analysis,  $\alpha = 0.044$  for the final analysis). If a participant drops out from the study, then he will be considered as a failure. Additional analyses will be conducted using logistic models to adjust for other clinical factors, such as age, hypertension, and COPD. Logistic regression will be used for the primary endpoint ( $y = 1$  if a composite outcome, otherwise  $y = 0$ ) analysis with the treatment group as the testing factor ( $x$ ). The following covariates will be included in the model: age ( $z_1$ ), hypertension ( $z_2$ ), and COPD ( $z_3$ ). Given the composite outcome probability  $p = p(y = 1|x, z_1, z_2, z_3)$ , the basic model is defined as follows:

$$\text{Logit}(p) = \ln\left(\frac{p}{1-p}\right) = \beta_0 + \beta_1 x + \beta_2 z_1 + \beta_3 z_2 + \beta_4 z_3$$

Odds ratio and 95% confidence interval (CI) will be presented using SAS PROC GENMOD or PROC LOGSTIC. If the coefficient for treatment effect is significant, then the null hypothesis will be rejected. Logistic models will be tested for goodness of fit. We will assess goodness-of-fit using the statistic -2 log likelihood, which has a  $\chi^2$

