## 3.9 Interim Analyses

A mid-term interim analysis of the primary endpoint will be performed when half of the participants (99 randomized participants) complete or are terminated from the study. If the mid-term analysis of the primary endpoint indicates that the null hypothesis can be rejected with a boundary value of 2.77 (standardized  $Z > 2.77$  or  $< -2.77$ ) at an  $\alpha$ -level of 0.006 or accepted with a boundary value of 0.44 ( $-0.44 \leq \text{standardized } Z \leq 0.44$ ) based on O'Brien and Fleming criteria, the study will be recommended for trial termination for efficacy and futility reasons (shown in Appendix 5.7). The number and percentage of participants with the composite endpoint at day 15 will be summarized and compared using Pearson  $\chi^2$  test (Table 3.9.1a) using SAS PROC FREQ. For

logistic regression analysis, if the coefficient for treatment effect is significant (i.e., the confidence interval for the odds ratio does not include 1), then the null hypothesis will be rejected. The significant level for each covariate coefficient in the model will best determined by Wald test (Table 3.9.1b) using SAS RPOC LOGISTIC. The analysis will be done in the ITT population. The detailed analysis is described in the primary endpoint analysis in the section 3.7.1.

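### SAP 3.6 allows the efficacy models to be adjusted for unnamed drugs taken after dosing when their use differs between arms, so a model may no longer estimate the whole randomised effect

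*SAP*

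**What the plan says.** SAP 3.6 defines concomitant drugs as "medications taken on or after the study drug administration" and tests every generic name and therapeutic class between arms with a Pearson chi-square. It sets no significance level of its own, so the general 0.05 of SAP 3.1.2 applies. The trigger for adjustment is a significant difference between arms in the use of some study-related drugs. Once it is met, the instruction is that "these concomitant medication use will be adjusted for the endpoint efficacy analyses when it is necessary". The section does not list the drugs, say when adjustment is needed, exempt an endpoint or set a time cut-off. On timing it says: "Concomitant medications will be reported at screening, day 8,15,22, and 30". Two of those visits fall after the Day 15 primary endpoint.

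The primary comparison in SAP 3.7.1 is unadjusted: "This outcome will be compared according to assigned treatment groups, using Pearson" chi-square. The same section adds a logistic model with age, hypertension and COPD, and attaches its own decision rule: "If the coefficient for treatment effect is significant, then the null hypothesis will be rejected". SAP 3.7.2 repeats that rule for the Cox models, and SAP 3.9 gives an equivalent one for the logistic model at the interim. SAP 3.7 states: "Both the primary and secondary endpoints analyses will be performed for the hypothesis testing".

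The protocol's statistical section contains no adjustment for concomitant medication. Protocol section 6 permits remdesivir, convalescent plasma, IL-6 antibodies and, for COVID-19, glucocorticoids during the study.

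**The concern.** Drug use after dosing can be an effect of treatment. The trial's hypothesis is that degarelix lessens the severity of illness. If it does, fewer degarelix patients may need the drugs given to patients who deteriorate. A real effect on drug use makes the significance trigger more likely to fire, and the adjustment then removes part of the effect under study. It can also add bias from causes shared by drug use and outcome. Chance imbalances, and drugs already running at dosing, are not consequences of treatment, but the rule does not separate them.

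Two things are at stake. First, the unadjusted test and the adjusted model can disagree on one endpoint while the SAP lets the model coefficient decide the null as well. Second, because the drugs and the condition are open, the model can be chosen after the arms have been compared on drug use.

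**Working it through.** **Inputs from the documents (SAP 2.6, 3.1.2, 3.7.1).** Event rates 60% placebo and 35% degarelix; 2:1 allocation; 186 evaluable (62 + 124) and 198 enrolled (66 + 132); sample-size alpha 0.05 two-sided; final alpha 0.044; trigger alpha 0.05.

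**The plan's own figure.** For a two-proportion test with pooled variance under the null, n(placebo) = [1.96·√(1.5·p̄(1−p̄)) + 1.2816·√(0.60·0.40 + 0.35·0.65/2)]² / 0.25², with p̄ = (0.60 + 2·0.35)/3 = 0.433. This is (1.190 + 0.762)²/0.0625 ≈ 61, so 61 + 122 = 183, within 2% of the stated 186. At 62 + 124 the power is 90.5%. The planning odds ratio is (0.35/0.65)/(0.60/0.40) = 0.359.

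**Assumptions.** The documents give no drug-use rates or drug effects. The cases below are calibrated to exactly 60% and 35%. Odds ratios are large-sample logistic fits of outcome on arm, with and without drug use. Power comes from 20,000 simulated trials of 66 versus 132, with Wald and Pearson tests at 0.044. Age, hypertension and COPD are omitted for simplicity.

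**One case by hand.** Suppose the whole benefit acts through prevented worsening, event risk is 90% if worse and 20% if not, and the drug is inert.

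- Worsening: placebo (0.60 − 0.20)/0.70 = 57.1%; degarelix (0.35 − 0.20)/0.70 = 21.4%.
- With use of 85% if worse and 25% if not: placebo 0.571·0.85 + 0.429·0.25 = 59.3%; degarelix 0.214·0.85 + 0.786·0.25 = 37.9%.
- Event risk among users: placebo 0.4586/0.5929 = 77.3%; degarelix 0.2032/0.3786 = 53.7%; odds ratio 0.34.
- Event risk among non-users: placebo 0.1414/0.4071 = 34.7%; degarelix 0.1468/0.6214 = 23.6%; odds ratio 0.58.
- The model combining the two strata gives 0.44, against 0.36 unadjusted.

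**Range of cases.** Use is shown as % if worse / % if not. Power compares the model never adjusted with the model always adjusted; a dash means not computed.

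| Case | Use | Odds ratio, unadjusted → adjusted | Model power |
|---|---|---|---|
| (a) whole benefit through worsening, inert drug | 50/20 | 0.36 → 0.38 | 92% → 87% |
| (a) | 85/25 | 0.36 → 0.44 | 91% → 67% |
| (a) extreme | 95/10 | 0.36 → 0.61 | 91% → 25% |
| (b) half the risk difference through worsening, inert drug | 85/25 | 0.36 → 0.36 | 91% → 84% |
| (c) drug odds ratio 0.4, event risks 80%/30% before the drug acts | 85/25 | 0.36 → 0.38 | – |
| (c) drug odds ratio 0.4 | 50/20 | 0.36 → 0.34 | – |
| (c) drug odds ratio 0.25 | 50/20 | 0.36 → 0.31 | – |
| (d) use follows the Day 15 outcome only | 70 with event / 40 without | 0.36 → 0.36 | 91% → 89% |

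**The rule as written, with its trigger.** In case (a) at 85/25, the trigger fires in 82% of trials, and in 22% Pearson is significant while the model is not. In case (a) at 50/20, it fires in about 35%, power under the rule is about 88%, and that disagreement occurs in about 4%. In case (b) the figures are about 30%, 87% and 4–5%.

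**A different set-up.** Fix use at 50% on placebo and 25% on degarelix, with use marking a worse outcome within each arm (odds ratio 2, 4 or 8). The adjusted treatment odds ratio is 0.417, 0.465 or 0.505. In 1,500 simulated trials, power falls from about 92% to 60% (marker odds ratio 4) or 49% (8). With equal use in both arms it is 0.348, 0.317 or 0.269, which is non-collapsibility only.

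**No treatment effect.** With one drug, rejection in favour of degarelix is about 2% with or without the rule. With k independent drugs and no true difference in use, the chance of at least one false trigger is 1 − 0.95^k: 23%, 40% and 64% for k = 5, 10 and 20 (k assumed).

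**The case against.** The strongest reply has five parts.

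- **The main tests are covariate-free.** Pearson, log-rank, Wilcoxon and Cochran-Armitage tests come first for every endpoint, and the regressions are described as additional. This is right and limits the reach. But SAP 3.7.1, 3.7.2 and 3.9 still let the logistic and Cox coefficients reject the null, so those models are not merely descriptive.
- **The models' own sections and Appendix 5.6 list only baseline covariates, and the hedged sentence in 3.6 may never be used.** It may not be. But 3.6 is worded for the efficacy analyses in general, and the hedge leaves the decision until the arms have been compared.
- **The large figures come from one corner of the assumptions.** This stands. With milder drug use, or half the effect through worsening, disagreement is about 4–5% of trials. Case (b) shows no shift in the odds ratio, only a loss of power, so movement toward no effect should be claimed only where the benefit acts mainly through prevented worsening. Case (d) shows that drug use driven by the Day 15 outcome does little harm.
- **The null case covers a single drug.** This also stands. Selection among several drugs, and rejection by either of two tests, were not quantified.
- **Disagreement between Pearson and a model with its own rejection rule is a separate defect.** It is: it would persist with baseline covariates alone, and the change below does not cure it.

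**Conclusion.** The concern holds. As written, 3.6 permits a data-triggered adjustment for unnamed post-dose drugs in models that the SAP uses to reject null hypotheses. That does not depend on any magnitude. The primary Pearson p-value is not affected.

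How far the model results move depends wholly on assumed drug use and drug effects. Where benefit acts through prevented worsening and the drug is inert, the odds ratio goes from 0.36 to between 0.38 and 0.61, and model power from 91–92% to between 87% and 25%; the lower end is extreme. With half the effect through worsening, the odds ratio is unchanged and power falls to 84% if the model is always adjusted, or about 87% under the rule. An effective drug can leave little shift or reverse it (0.31). For a single drug there is no sign of type I error inflation. The text should be changed before analysis, but the trial's primary conclusion does not hang on it.

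**What to change.** Replace the last sentence of SAP 3.6 with:

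> Medications started on or after dosing will be tabulated by arm and will not enter the efficacy models used for hypothesis testing; any medication adjustment is limited to medications started before randomisation and named before unblinding. Any analysis involving post-dose medications will be a pre-specified, labelled sensitivity analysis.

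The protocol's Blinding section lets the study biostatisticians see assignments as needed, so the naming should be done before anyone tabulates drug use by arm. The cost is one SAP passage, no new data and slightly less programming.

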### 3.7 Efficacy Analyses

The primary analysis of the study will be performed on the primary endpoint on the ITT population. The secondary analyses will be performed on the ITT population and available data. Both the primary and secondary endpoints analyses will be performed for the hypothesis testing. While the exploratory endpoints will be analyzed to generate new hypothesis unless otherwise specified. Potential difficulties of convergence of model fit, which arise in efficacy analyses that include covariates, will be handled using the method described in section 3.7.1. The analysis plan is summarized in the Appendix 5.6.

#### 3.7.1. Primary Endpoint Analysis

The primary study endpoint will be the composite outcome of mortality, ongoing need for hospitalization, and ECMO or mechanical intubation at 15 days after randomization. This outcome will be compared according to assigned treatment groups, using Pearson  $\chi^2$  test. The test for differences between the treatment groups in the primary outcome will be conducted at an overall  $\alpha$ -level of 0.05 (i.e.  $\alpha = 0.006$  for mid-term interim analysis,  $\alpha = 0.044$  for the final analysis). If a participant drops out from the study, then he will be considered as a failure. Additional analyses will be conducted using logistic models to adjust for other clinical factors, such as age, hypertension, and COPD. Logistic regression will be used for the primary endpoint ( $y = 1$  if a composite outcome, otherwise  $y = 0$ ) analysis with the treatment group as the testing factor ( $x$ ). The following covariates will be included in the model: age ( $z_1$ ), hypertension ( $z_2$ ), and COPD ( $z_3$ ). Given the composite outcome probability  $p = p(y = 1|x, z_1, z_2, z_3)$ , the basic model is defined as follows:

$$\text{Logit}(p) = \ln\left(\frac{p}{1-p}\right) = \beta_0 + \beta_1 x + \beta_2 z_1 + \beta_3 z_2 + \beta_4 z_3$$

Odds ratio and 95% confidence interval (CI) will be presented using SAS PROC GENMOD or PROC LOGSTIC. If the coefficient for treatment effect is significant, then the null hypothesis will be rejected. Logistic models will be tested for goodness of fit. We will assess goodness-of-fit using the statistic -2 log likelihood, which has a  $\chi^2$

distribution under the null hypothesis that all the explanatory variables in the model are zero. We will also consider the Akaike Information Criterion statistic and the Schwartz Criterion statistic, both of which adjust the -2-log likelihood for the number of items in the model. Models that show lack of fit will be reconsidered for the inclusion of additional variables or use of alternate models with assumptions that are better met by the study data. One alternate model if model fit is poor for logistic regression is a log-linear model. The number and percentage of participants with the composite endpoint at the 15 day after the randomization will be summarized and compared using Pearson  $\chi^2$  test (Table 3.7.1a). For logistic regression analysis, if the coefficient for treatment effect is significant (i.e., the confidence interval for the odds ratio does not include 1), then the null hypothesis will be rejected. The significant level for each covariate coefficient in the model will best determined by Wald test (Table 3.7.1b). Meanwhile, Cochran Mantel-Haenszel test will be used to adjust for three randomization stratification factors (Age: <65 vs.  $\geq$ 65, History of hypertension: yes vs. no, and Influenza severity scale: 3 vs 4/5) using SAS PROC FREQ as one of the sensitivity analyses (Table 3.7.1c).

